4.2 Exclusion Criteria

1. Subjects who have received any cytotoxic chemotherapy within the last 7 days prior to biopsy
2. Subjects who have received any radiotherapy to the primary sample site within the last 14 days (radiation may be included in treatment decision after biopsy).
3. Subjects receiving any investigational drug concurrently.
4. Subjects with uncontrolled serious infections or a life-threatening illness (unrelated to tumor)
5. Subjects with any other medical condition, including malabsorption syndromes, mental illness or substance abuse, deemed by the Investigator to be likely to interfere with the interpretation of the results or which would interfere with a subject's ability to sign or the legal guardian's ability to sign the informed consent, and subject's ability to cooperate and participate in the study

Additional criteria:

Subjects willing to participate in the correlative biologic studies will sign an additional consent form to provide additional tumor tissue.

5 STUDY PROCEDURES AND ASSESSMENTS

5.1 Enrollment of Subjects

All subjects (or subjects' legal representatives) must provide written informed consent before any study specific assessments may be performed. The NMTRC will keep a "possible enrollment list" for all sites combined. Subjects will be allowed to enroll in the order that they are added to that list. Prior to consent of the subject, the NMTRC research coordinator will be contacted (via e-mail) to place subject on this possible enrollment list. The NMTRC coordinator will then reply with study space availability. If a spot is not available at that time, the site will be contacted as soon as a spot does open up (based on the subject's order on the list). If a spot is available at the time, the potential subject will undergo consent and completion of all required screening procedures and certification of all inclusion and exclusion criteria by the Investigator. If the subject fits all enrollment criteria, the site will again contact the coordinator at the NMTRC for official enrollment confirmation and unique subject identifier assignment. In addition, a study enrollment form will be e-mailed or faxed to the coordinator at the NMTRC. A subject may NOT be enrolled on trial until official approval from the NMTRC is received. When a spot becomes available, the first subject from the list will be contacted and will have 5 working days with which to enroll in the study. If this subject does not enroll by that time then the subject forfeits his/her spot and the next subject will be offered that spot.

5.2 Screening

The Investigator is responsible for keeping a record of all subjects screened for entry into the study and subsequently excluded.

The following screening procedures must be performed within 21 days (14 days preferred) prior to date of biopsy*. Studies must be done *after* last previous treatment for malignancy:

1. Signed informed consent form. All subjects (or subjects' legal representatives) must provide written informed consent before any study specific assessments may be performed. Signed informed consent form for voluntary participation in correlative biologic analysis;
2. Complete medical and surgical history, including documentation of the evidence of malignancy and prior treatments for cancer. Include all other pertinent medical conditions and a careful history of all prior medical treatments;
3. Demographics;
4. Physical examination (including height and weight), noting all abnormalities and sites of palpable neoplastic disease;
5. Vital signs, including temperature, pulse rate, and blood pressure;
6. Karnofsky Performance status/Lansky Play status (Appendix I);
7. Complete Screening Baseline Symptom form;
8. CBC with differential;
9. Serum electrolytes (sodium, potassium, chloride, bicarbonate), blood urea nitrogen (BUN), creatinine, albumin, Bilirubin, ALT, and AST;
10. LDH and/or Specific Tumor Markers for defined disease (if available);
11. Serum pregnancy test for female subjects of child bearing potential (onset of menses or \geq 13 years of age);
12. CT or MRI of measurable disease sites (as indicated for tumor type);
13. Solid tumor biopsy for "Primary Sample" with remaining tumor tissue used in correlative biologic studies handled per section 9.3 and submitted per Appendix II.

For subjects that cannot provide a solid tumor biopsy; a bone marrow core biopsy sample will replace the solid tumor sample as the "Primary Sample." Bone Marrow must have adequate tumor (defined as >50% tumor) in order to qualify as "Primary Sample."

***NOTE: If standard-of-care sample collection occurred within 12 weeks prior to enrollment and after last previous treatment for malignancy, and frozen sample remains, a subject may enroll using previously collected samples. Samples must additionally have been snap frozen within 20 minutes of collection and kept in a -70/-80 freezer.**

14. Concomitant medications/therapies including documentation of steroid use and dose;
15. Confirmation of inclusion and exclusion requirements.

Following completion of all required screening procedures and certification of all inclusion and exclusion criteria by the Investigator, the coordinator at the NMTRC will be contacted (via e-mail or phone call), at which time the subject will be enrolled in the trial and a unique subject number assigned.

The following screening procedures must be done prior to the first dose of study drug, but are not required to be done before biopsy.

1. MIBG/PET scan (if indicated for tumor type). Other imaging appropriate for tumor type may also be considered.
2. Any subject that is suspected to have possible bone marrow disease: Bone marrow aspirate and biopsy.
3. Completion (by study staff) of pre-study case report forms.
4. Any additional labs or testing required by the tumor board.

For subjects that receive one cycle of treatment while waiting to start tumor board defined treatment (per section 2.11) or if patient did not receive treatment but more than 28 days since last assessment has occurred prior to starting study treatment: The following additional screening procedures must be performed AFTER the last dose of this additional cycle of therapy and PRIOR to the first dose of tumor board defined treatment:

1. Repeat CT or MRI of primary disease sites and any disease sites being followed for study endpoints.
2. CBC with differential- subject must be hematologically recovered to baseline before starting tumor board defined treatment.

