- x. Ethesioneuroblastoma (At relapse after standard of care therapy and/or non- responsive/progressive to accepted curative chemotherapy).
- xi. Neuroendocrine tumors (At relapse after standard of care therapy and/or non- responsive/progressive to accepted curative chemotherapy).
- xii. Desmoplastic small round cell tumor (At relapse after standard of care therapy and/or non- responsive/progressive to accepted curative chemotherapy).
- xiii. Melanoma (At relapse after standard of care therapy and/or non- responsive/progressive to accepted curative chemotherapy).

2. Subjects must be age \geq 12 months at enrollment
3. Subjects must be age \leq 21 years at initial diagnosis
4. Subjects must have measurable disease as defined by RESIST v1.1 at the time of biopsy and tumor must be accessible for biopsy. Tumor samples submitted for analysis must contain $>50\%$ viable tumor tissue to qualify. In addition, subjects with disease confined to the bone marrow are eligible to enroll if the degree of marrow involvement is expected to be $>50\%$.
Note: Subjects who are expected to have no evidence of disease after surgical removal of their tumor are still eligible for this trial if their disease would normally require adjuvant chemotherapy treatment after surgery despite NED status.
5. Current disease state must be one for which there is currently no known effective therapy
6. Specimens will be obtained only in a non-significant risk manner and not solely for the purpose of investigational testing.
7. Lansky or Karnofsky Score must be ≥ 50
8. Subjects without bone marrow metastases must have an ANC $> 750/\mu\text{l}$ to begin treatment.
9. Subjects with CNS disease currently taking steroids must have been on a stable dose of steroids for 2 weeks prior to their biopsy and must not have progressive hydrocephalus at enrollment.
10. Adequate liver function must be demonstrated, defined as:
 - a. Total bilirubin $\leq 1.5 \times$ upper limit of normal (ULN) for age AND
 - b. ALT (SGPT) $< 10 \times$ upper limit of normal (ULN) for age
11. A negative serum pregnancy test is required for female participants of child bearing potential (≥ 13 years of age or after onset of menses)

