12. Both male and female post-pubertal study subjects need to agree to use one of the more effective birth control methods during treatment and for six months after treatment is stopped. These methods include total abstinence (no sex), oral contraceptives ("the pill"), an intrauterine device (IUD), levonorgestrel implants (Norplant), or medroxyprogesterone acetate injections (Depo-provera shots). If one of these cannot be used, contraceptive foam with a condom is recommended.

13. Informed Consent: All subjects and/or legal guardians must sign informed written consent. Assent, when appropriate, will be obtained according to institutional guidelines

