5.3 Study Procedures/Study Interventions

5.3.1 Study Visits- Cycle 1 Day 1 (may have been done within 5 days of treatment start/day 1, unless otherwise indicated as “same day”)

Subjects will return to the enrolling clinic at Day 1 of cycle 1 for evaluations. The following evaluations will be conducted prior to starting study drug:

1. Physical examination (including body weight) and medical history (**same day**);
2. Karnofsky Performance status/Lansky Play status-Appendix I (**same day**);
3. Vital signs, including height, weight, temperature, pulse rate, and sitting blood pressure (**same day**);
4. CBC with differential;
5. Serum electrolytes, BUN, creatinine, Bilirubin, ALT, AST;
6. LDH and/or Specific Tumor Markers for defined disease (if available);
7. Baseline EKG (as indicated);
8. Cycle 1 Day 1 Baseline Symptom Form (**same day**);
9. Review and recording of concomitant medications (**same day**);
10. Completion (by study staff) of Case Report Forms;
11. Any additional labs or testing required by the tumor board.

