5.3.7 Off Therapy/30 Day Follow-Up Visit

Subjects will be followed up at either the study clinic or by telephone within 30 (+7) days after the last dose of treatment. Last dose of treatment is defined as the last day that the subject received a tumor board recommended treatment. The following evaluations will be conducted:

1. Review and recording of concomitant medications;
2. Monitoring of AEs and review of concurrent illnesses;
3. Completion (by study staff) of Case Report Forms.

Any subject with suspected study drug related toxicities at the follow-up visit must be followed until all current drug related adverse events have resolved to baseline or \leq Grade 2 or stabilization of the event. This may require additional clinical assessments and laboratory

tests. The follow-up results will be recorded on the appropriate page of the CRF, as well as in the subject's source documentation.

6 Protocol Drugs

Specific treatment details will consist of a regimen chosen from a guided list of agents implicated in critical molecular signaling pathways and/or from signature-based predictions of drug efficacy summarized from the guided therapy report. All agents are listed in the current pharmacopoeia for human use, but will differ amongst individual subjects. The treatment regimens will be discussed with families and will include review of known side effects per Pharmacopeia Library (Appendix III) (information obtained from package insert and from MicroMedex, LexiComp, Facts and Comparisons, and Natural Medicines Database), serious adverse effects of possible new drug combinations, and any additional clinical monitoring that may be recommended by the tumor board. The family will be given the option to proceed with therapy and if the family decides to proceed with the tumor board's treatment decision they will be asked to sign a treatment specific memo.

Drugs will be prescribed by the enrolling institution per treating hospital protocol and administered per FDA guidelines and tumor board recommendations.

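### The serum pregnancy test is scheduled once, at screening, and the protocol names no repeat before the first dose

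*Combined protocol and SAP*

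**What the plan says.** Inclusion criterion 11 (Section 4.1) makes the test a condition of entry: "A negative serum pregnancy test is required for female participants of child bearing potential". The criterion gives no timing relative to dosing. The timing comes from Section 5.2, where item 11, "Serum pregnancy test for female subjects of child bearing potential", sits in the list headed "The following screening procedures must be performed within 21 days (14 days preferred) prior to date of biopsy". A note to that list lets a subject enroll on a stored standard-of-care sample taken up to 12 weeks before enrollment. On that route the test can only fall at screening for enrollment.

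Section 5.2 has a second list, of procedures that "must be done prior to the first dose of study drug, but are not required to be done before biopsy". It contains MIBG/PET imaging, bone marrow, case report forms and any tumor-board tests. A third list applies after a bridging cycle, or when more than 28 days have passed since the last assessment. It repeats CT/MRI and CBC. Section 5.3.1 introduces the Cycle 1 Day 1 list with "The following evaluations will be conducted prior to starting study drug" and gives 11 items. None of these three lists names a pregnancy test, and the Table of Procedures marks B-HCG under Screening alone.

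Inclusion criterion 12 asks for effective "birth control methods during treatment and for six months after treatment is stopped".

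**The concern.** The plan treats fetal exposure as a risk to be avoided: it wants a negative test at entry and contraception until six months after treatment. Neither safeguard, as written, covers the wait between the screening test and the first dose. The test lies behind the subject, and the contraception requirement is worded around treatment and its aftermath.

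Elsewhere the plan accepts that baseline information ages. The neutrophil criterion ("Subjects without bone marrow metastases must have an ANC" above 750/μl) applies at the start of treatment, CBC and chemistry are redone within 5 days of Day 1, and imaging and CBC are redone after 28 days. The pregnancy test is not handled in the same way.

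A subject who becomes pregnant during the wait could therefore complete every scheduled procedure and begin a combination of up to four drugs with the pregnancy undetected, unless a regimen-specific check picks it up. Those at risk are females of child-bearing potential, in a trial that takes patients diagnosed up to age 21.

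**Working it through.** The plan gives no figure to reproduce. The check has two parts: where the test appears, and how old it can be at first dose.

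**Where the test appears**

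- Pre-biopsy screening list (Section 5.2): yes, item 11.
- Procedures due before first dose (Section 5.2): no.
- Repeats after bridging therapy or more than 28 days (Section 5.2): no; CT/MRI and CBC only.
- Cycle 1 Day 1 (Section 5.3.1): no. CBC and chemistry are on this list, so blood is already drawn.
- Cycle 1 Days 8, 15 and 22, and subsequent cycles (Sections 5.3.2 to 5.3.5): no.
- Table of Procedures: B-HCG at Screening only.

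Three of these lists (before first dose, Day 1 and later visits) include any tests the tumor board asks for. That item can bring in a pregnancy test but does not name one.

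**Limits on the wait**

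- Section 9.6 limits two steps: the tumor board meets within 4 days of receiving the report, and treatment begins within 1 week of the discussion with parents.
- No limit is stated for sequencing and report generation, or for the total from biopsy to first dose.
- The Section 8 feasibility definition has no day limit. Section 12.3 refers to overall time frame limits without giving one for this interval.
- Section 3.6 allows one bridging cycle between biopsy and study treatment, of unstated length.

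**Age of the test at first dose**

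Age = (days from test to biopsy) + (days from biopsy to first dose).

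- Test to biopsy: 0 to 21 days, 14 preferred (Section 5.2).
- Biopsy to first dose: 7 to 20 days, mean 12.4, from the earlier neuroblastoma feasibility trial in Section 1.2. This is an assumption here: that trial used gene chips rather than sequencing, and its feasibility definition carried a 21-day limit that this trial lacks.

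| Test taken | Treated 7 days after biopsy | Treated at the mean, 12.4 days | Treated 20 days after biopsy |
|---|---|---|---|
| Day of biopsy | 0 + 7 = 7 | 0 + 12.4 = 12.4 | 0 + 20 = 20 |
| 14 days before (edge of preferred window) | 14 + 7 = 21 | 14 + 12.4 = 26.4 | 14 + 20 = 34 |
| 21 days before (edge of allowed window) | 21 + 7 = 28 | 21 + 12.4 = 33.4 | 21 + 20 = 41 |

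The range without bridging therapy is 7 to 41 days. The second and third rows are window edges, not typical values. A test taken 21 days before biopsy is more than 28 days old whenever treatment starts later than day 7 (21 + 7 = 28). Past 28 days since the last assessment, the plan itself asks for new imaging and a new CBC.

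If a bridging cycle began at once after biopsy and lasted 21 to 28 days (assumed), the test would be 0 + 21 = 21 to 21 + 28 = 49 days old, before any time for hematologic recovery.

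The table does not apply to the stored-sample route, where the biopsy can precede enrollment.

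With the test moved into the Day 1 window of Section 5.3.1, its age at first dose is at most 5 days.

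**The case against.** The strongest reply is that regimens are individual, so drug-specific testing belongs with the people who choose the drugs. The safeguards are real. Section 3.1.2 requires a 12-hour safety review and pharmacist sign-off on every final regimen. Section 1.2 says pharmacy review, including the choice of laboratory and safety tests, will continue in this trial. Any test the board requires is due before first dose. Section 6 adds a binding clause: "Drugs will be prescribed by the enrolling institution per treating hospital protocol and administered per FDA guidelines and tumor board recommendations". A same-day history and examination also precede dosing.

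Much of this stands. A reader might infer that nothing after screening obliges anyone to repeat the test. The documents do not support that: hospital protocols and the FDA guidelines for a chosen drug may require one, and those sources are not in the documents. What can be said is that the protocol names no repeat and sets no uniform rule across regimens and sites. History and examination do not close the gap, since the plan lists both at screening and still asks for a serum test.

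Three other readings also go too far.

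- The wait is not wholly open-ended, because Section 9.6 limits two steps. Only the total is unlimited.
- The test does not always precede biopsy, because of the stored-sample route. In addition, Section 3.2 applies all requirements afresh when a further biopsy leads to a new regimen.
- The ages in the table are not risks. The documents give no basis for a pregnancy rate or a count of affected subjects.

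**Conclusion.** The point holds as a scheduling gap in a safety check. A subject can follow the written schedule exactly and start up to four drugs on a pregnancy test about 7 to 41 days old, or older after a bridging cycle. The range rests on the 0-21 day screening window, which the plan states, and on a 7-20 day biopsy-to-treatment interval borrowed from an earlier trial on a different platform. The finding that no repeat is named rests on the text alone and needs no assumption.

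A reader might take this as a threat to the trial's results. It is not: the gap concerns one subgroup and alters no endpoint, test or sample size. Because regimen-specific review may already catch some cases, this is a cheap improvement to make at the next amendment and not a failure of the design.

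**What to change.** Add serum B-HCG for females of child-bearing potential to the Cycle 1 Day 1 list in Section 5.3.1 and to the Cycle 1 Day 1 column of the Table of Procedures. Use the existing 5-day window and the blood already drawn for CBC and chemistry, and require a negative result before the first dose. Keep the screening test for eligibility.

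State how a positive Day 1 result is handled. The subject does not start study treatment, and under the existing Section 8 feasibility definition she is counted as not having started. Without that sentence, she might be dropped as ineligible at one site and counted as a failure at another.

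The cost is one line of text, one Table cell, the handling sentence, and one extra assay in a subgroup. The downside is an occasional subject who cannot start and so does not meet the feasibility definition. Section 8 records the feasibility measures as already met in all strata by Amendment 3.0, so such a case would affect the further feasibility data from the second 100 subjects and not that recorded result.

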3.6 Treatment during waiting period

Subjects will be allowed to receive one cycle of standard of care or treating physician chosen therapy after their biopsy and before starting tumor board defined therapy in order to prevent progression during this waiting period. Subjects that opt to have this cycle of therapy will need to have recovered from hematological effects (to baseline) and have repeat scans of their primary tumor sites and any sites being followed for study efficacy before starting tumor board defined therapy.

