- **Progressive Disease (PD):** At least a 20% increase in the sum of the disease measurements for measurable lesions, taking as reference the smallest disease measurement recorded since the start of treatment (nadir), and minimum 5 mm increase over the nadir or the appearance of one or more new lesions.

Response Criteria for Subjects with Bone Marrow Disease:

- Those subjects with morphologic evidence of disease by routine H and E staining (NSE staining only is not evaluable) will be evaluable to assess bone marrow response.
- **Complete response:** No tumor cells detectable by routine morphology on two consecutive bilateral bone marrow aspirates and biopsies done at least three weeks apart after study entry.
- **Progressive disease:** Tumor seen on morphology on two consecutive bone marrows done at least three weeks apart in subjects who had NO tumor in bone marrow at study entry. (Note: Subject may be declared as progressive disease in bone marrow after only one diagnostic bone marrow at the discretion of the treating physician after discussion with the study chair.)
- **Stable disease:** Persistence of an amount of tumor in the bone marrow by morphology that does not meet criteria for either complete response or progressive disease.

Response Criteria for Subjects with MIBG or PET Positive Lesions

- Subjects who have a positive MIBG or PET scan at the start of therapy will be evaluable for MIBG or PET response. All MIBG's and PET scans will be performed at the research institution and then centrally reviewed.
- **Complete response** = complete resolution of all positive lesions
- **Partial response** = resolution of at least one positive lesion, with persistence of other MIBG positive lesions.
- **Stable disease** = no change in scan in number of positive lesions (includes subjects who have same number of positive lesions but decreased intensity)
- **Progressive disease** = Development of new positive lesions

The intensity of MIBG uptake is not to be considered in the above institutional evaluation.

Duration of response:

Duration of response is defined as the period of time from when measurement criteria are met for complete response (CR) or partial response (PR), whichever is first recorded, until the first date that recurrent or progressive disease (PD) is objectively documented (taking as reference for PD the smallest measurements recorded since the treatment started).

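### Sections 3.6 and 5.2 disagree on re-baselining after a bridging cycle and neither requires a marrow, so MIBG/PET or marrow clearance during bridging can be credited to tumor-board therapy

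*Combined protocol and SAP*

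**What the plan says.** Section 3.6 opens the window: "Subjects will be allowed to receive one cycle of standard of care or treating physician chosen therapy after their biopsy", before tumor-board therapy starts. Subjects who use it must recover hematologically and "have repeat scans of their primary tumor sites and any sites being followed for study efficacy before starting tumor board defined therapy". No modality is named, and marrow is not mentioned.

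Section 5.2 turns this into a list for sites. Two procedures must follow bridging and precede tumor-board treatment: "Repeat CT or MRI of primary disease sites and any disease sites being followed for study endpoints", and a CBC with differential. The list refers to a section 2.11 for the bridging rule. Section 2 ends at 2.5, and the rule is in 3.6. A separate list in 5.2 covers the MIBG/PET scan and, where marrow disease is suspected, the aspirate and biopsy. These "must be done prior to the first dose of study drug, but are not required to be done before biopsy". Their timing is not tied to the bridging cycle.

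The Cycle 1 Day 1 visit (5.3.1) includes neither MIBG/PET nor marrow by name, and the Table of Procedures and Assessments shows both at screening only.

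Section 7.3 uses both for response. For MIBG/PET, "Subjects who have a positive MIBG or PET scan at the start of therapy will be evaluable for MIBG or PET response"; PR needs one positive lesion to resolve while others persist, and CR needs all to resolve. Marrow CR needs no tumor on "two consecutive bilateral bone marrow aspirates and biopsies done at least three weeks apart after study entry". Clinical response also includes complete clearing of a previously positive marrow while on study.

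**The concern.** ORR is meant to show the activity of the treatments the tumor board chooses. That requires a baseline taken after any other anticancer therapy has ended. If the only MIBG/PET scan or marrow predates a bridging cycle, the change from that baseline combines the effects of bridging and of tumor-board therapy, and the data in that modality cannot separate them.

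Any subject followed by MIBG/PET or marrow is exposed, which points mainly to the 50-subject neuroblastoma stratum. The clearest case is disease confined to the marrow, which inclusion criterion 4 admits. In these subjects the marrow core is the Primary Sample, so a positive marrow exists before bridging by design. CT or MRI cannot re-baseline marrow-only disease.

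ORR is also compared between the first 100 patients and those enrolled after Amendment 3.0. If the share of subjects with only a pre-bridging baseline differs between cohorts, part of any ORR difference could reflect bridging rather than the updated Drug Prediction Report.

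**Working it through.** The plan states no figure on this point, so the check compares sections.

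| Question | 3.6 | 5.2 |
|---|---|---|
| CT/MRI after bridging? | Yes, as scans | Yes, named |
| MIBG/PET after bridging? | Can be read as yes: scans of any followed site | Not listed; any time before first study dose |
| Marrow after bridging? | Not mentioned | Not listed; any time before first study dose |

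Section 7.2 counts CT, MRI, MIBG and PET as study scans, so 3.6 can be read to include MIBG/PET. For MIBG/PET, then, the two sections conflict. For marrow, both are silent.

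**How bridging clearance reaches a response category**

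1. MIBG/PET: a lesion positive before bridging, cleared by it and still clear at the end-of-cycle-2 reassessment (5.3.6) meets the PR wording if other lesions persist. If all have cleared, it meets CR.
2. Marrow CR: one clear marrow is not enough. Two consecutive clear marrows at least three weeks apart are needed. On the 5.3.6 schedule, clearance would normally have to last from the end of cycle 2 to the next scheduled marrow.
3. Clinical response: 7.3 accepts complete clearing of a positive marrow while on study. The synopsis words this as CR of marrow. A responder in the synopsis is a subject with CR or PR, so this route affects the clinical-response rate.

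No section excludes change that occurred during bridging, and 12.4 reports ORR without separating bridged subjects. CT/MRI differs: 5.2 obtains a post-bridging image that can serve as reference.

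**Illustration of scale (not an estimate)**

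Let p be the true ORR on tumor-board therapy. Let f be the share of the stratum that is bridged with only a pre-bridging MIBG/PET or marrow baseline. Let r be the share of those with a countable clearing from bridging. If bridging clearance is independent of later response, and response in one modality makes the subject a responder:

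observed ORR = p + (1 − p) × f × r

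The documents give neither p nor f; the values below are assumed. The range r = 10% to 35% is borrowed from section 1.2, where it describes studies in relapsed neuroblastoma, not one cycle and not these modalities. The stratum size of 50 is from the synopsis.

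| p | f | r | (1 − p) × f × r | Observed ORR | Extra responders of 50 |
|---|---|---|---|---|---|
| 20% | 0 | any | 0 | 20.0% | 0 |
| 20% | 25% | 10% | 0.80 × 0.25 × 0.10 = 0.020 | 22.0% | 1.0 |
| 20% | 25% | 35% | 0.80 × 0.25 × 0.35 = 0.070 | 27.0% | 3.5 |
| 20% | 50% | 10% | 0.80 × 0.50 × 0.10 = 0.040 | 24.0% | 2.0 |
| 20% | 50% | 35% | 0.80 × 0.50 × 0.35 = 0.140 | 34.0% | 7.0 |

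With p and r equal in the two cohorts, the spurious ORR difference is (1 − p) × r × (f₂ − f₁), where f₁ and f₂ are now shares of each cohort. It is zero when the shares are equal and can take either sign.

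**The case against.** The strongest reply is that the plan already covers MIBG/PET. Section 3.6 asks for repeat scans without limiting modality, 7.2 counts MIBG and PET as scans, and 7.3 ties MIBG/PET evaluability to a positive scan at the start of therapy. A scan taken a full cycle earlier arguably does not show that. This largely stands. A reader might infer from 5.2 alone that no post-bridging MIBG/PET scan is ever obtained, so that the endpoint is beyond repair. The documents do not support that: nothing says 5.2 overrides 3.6, and a site may time the scan after bridging and comply with both. The remaining fault is that 5.2 is the more specific instruction, carries a broken cross-reference and does not define start of therapy relative to bridging.

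A second reply is that 5.2 requires studies to follow the last previous treatment. That sentence heads the pre-biopsy list, whereas bridging comes after biopsy and the MIBG/PET and marrow list has its own timing rule. It shows that the plan accepts the principle, but does not apply it here.

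A third is that marrow response is protected by the two-marrow rule. A reader might infer that one clear marrow at the end of cycle 2 is scored as PR or CR. It is not: marrow has no PR category, and CR needs the second clear marrow. The rule removes transient clearing but does not show which therapy produced a lasting one.

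Finally, 7.3 gives no rule for combining modalities, so an MIBG/PET or marrow response alone may not make an overall response. That is correct, and is one more reason not to put a number on the bias.

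**Conclusion.** The point holds as a contradiction between 3.6 and 5.2 for MIBG/PET and as a gap in both for marrow. Followed to the letter, 5.2 permits a pre-bridging baseline in either modality, and 7.3 and 12.4 then allow bridging clearance to be credited to tumor-board therapy. The gap is plainest for marrow-only subjects.

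It affects secondary ORR, clinical response, duration of any response so credited, and the ORR comparison between cohorts. Primary feasibility is untouched, since its definition contains no response component.

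The size is unknown. A reader might multiply an assumed bridged share of 20% to 60% by the 10% to 35% in section 1.2 and report 2 to 21 percentage points (0.20 × 0.10 to 0.60 × 0.35). The documents do not support that range. They give no bridging share, the response rates are not for one cycle or these modalities, the product counts subjects who would have responded anyway, and the lower limit must be 0 because sites that test after bridging have no such bias. Nor do the documents show that bridging use differs between cohorts; they only leave the possibility unexamined.

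**What to change.** 1. Reconcile 5.2 with 3.6 on which modalities the post-bridging re-baseline covers, say whether marrow is included, and correct the reference to section 2.11.
2. In 7.3, state that in a bridged subject an MIBG/PET or marrow response is credited to study therapy only against a same-modality baseline obtained after the last bridging dose.
3. In 12.4, report ORR by bridging status, overall and within each 100-patient cohort. Add a sensitivity analysis that keeps subjects without such a baseline in the denominator as non-responders in that modality.
4. Report by cohort how many bridged subjects lack a post-bridging MIBG/PET or marrow baseline.

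The cost is wording in three sections and a few tables. The analysis rule requires no added procedure: MIBG/PET (if indicated) and marrow (if disease is suspected) are already required before the first study dose and can be timed after bridging. In marrow-only subjects, the Primary Sample marrow cannot serve as that baseline because it precedes bridging.

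The real downside is lost evaluability. Every bridged subject without a post-bridging baseline drops out of the response analysis in that modality, so the number lost equals the number affected. This may fall more heavily on the first cohort, already enrolled when Amendment 3.0 was written, because clearer wording can improve baselines only from now on. The sensitivity analysis and the counts by cohort are there to show whether this selective loss changes the comparison.
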